## 7.2 Analysis for Secondary Outcomes

Analysis of secondary outcomes will be primarily descriptive. The distribution of swallowing function and mucositis scores will be summarized by arm using means, medians, standard deviations, and ranges. The objective response rate will be estimated by arm along with an exact 95% binomial confidence interval.

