### 1.1 Specific Aims and Hypothesis

**Purpose of the study:** To assess the effect of metformin on inflammatory pathways in subjects with cancer of the head and neck undergoing external beam radiation. We will use analysis of cytokines/chemokine profiles expression and exosome profiles in subjects that receive metformin during their radiation treatment.

- **Primary objective:** Assess the impact of metformin on cytokine/chemokine and exosomes on blood and saliva during and after radiation.
- **Secondary objectives:** Assess safety and tolerability of metformin treatment in subjects with head and neck cancer. Also, to assess the potential impact of metformin on the following: xerostomia, dysphagia, mucositis, fatigue as measured by EORTC QLQ – H&N35, Xerostomia Score, mucositis score and Multidimensional Fatigue Inventory (MFI) (See appendix).

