### **2.2 Secondary Objective:**

- Assess safety and tolerability of metformin treatment in subjects undergoing external beam radiation treatment for head and neck cancer.

- To determine the effect of metformin treatment on symptoms of **xerostomia** as assessed by the Xerostomia Questionnaire (XQ)
- To determine the effect of metformin treatment on symptoms of **mucositis** as assessed by WHO classification
- To determine the effect of metformin treatment on symptoms of **dysphagia** as assessed by the MD Anderson Dysphagia Inventory
- To determine the effect of metformin treatment on symptoms of **Fatigue** as assessed by the Multidimensional fatigue inventory (MFI).

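### Section 7.2 names a summary for only two of the five secondary objectives and plans no between-arm estimate for any, so the prespecified analysis does not answer the stated aim on symptoms

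*Combined protocol and SAP*

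**What the plan says.** Section 2.2 lists five secondary objectives. The first reads "Assess safety and tolerability of metformin treatment in subjects undergoing external beam radiation treatment for head and neck cancer". The other four are each worded as determining what metformin does to a symptom, and each names an instrument:

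- xerostomia, "as assessed by the Xerostomia Questionnaire (XQ";
- mucositis, "as assessed by WHO classification";
- dysphagia, "as assessed by the MD Anderson Dysphagia Inventory";
- fatigue, "as assessed by the Multidimensional fatigue inventory (MFI".

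Section 1.1 puts the aim more softly: "to assess the potential impact of metformin on the following: xerostomia, dysphagia, mucositis, fatigue". Section 2.4 lists the four symptoms as endpoints, and section 2.5 makes CTCAE toxicity the primary safety endpoint.

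Section 7.2 begins "Analysis of secondary outcomes will be primarily descriptive" and then specifies: "The distribution of swallowing function and mucositis scores will be summarized by arm using means, medians, standard deviations, and ranges". The only interval it plans is a per-arm exact binomial interval for objective response, which sections 2.1 to 2.5 do not list as an objective or endpoint. The Study Summary gives the same limited plan. The only between-arm contrast in section 7 is in 7.1, for cytokines and exosomes. Section 8 covers the definition, recording, reporting and monitoring of adverse events, not their comparison between arms.

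**The concern.** In a 1:1 randomized trial, the effect of a treatment is a difference between arms. Four objectives ask for such an effect, and sections 1.6 and 3.0 also present the trial as evaluating whether metformin mitigates the consequences of radiation. Followed as written, 7.2 produces arm-level summaries of two outcomes at unstated visits. It produces no effect estimate and no statement of uncertainty.

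Two things are at stake. First, readers would compare arm means by eye, with 25 patients per arm, and could take noise for signal. Second, the choice of outcome, visit and summary stays open until the data are seen. That matters more here because section 5.9 leaves the principal investigator and the care providers who make assessments unblinded.

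**Working it through.** **1. Objectives set against the analysis plan**

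| Objective (2.2) | Summary named in 7.2 | Arm difference or interval |
|---|---|---|
| Safety and tolerability | None | None |
| Xerostomia (XQ) | None | None |
| Mucositis (WHO) | By-arm mean, median, SD, range | None |
| Dysphagia (MD Anderson inventory) | Same, if swallowing function means this inventory | None |
| Fatigue (MFI) | None | None |

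Two of five have a named summary, three have none, and none has a between-arm estimate. The count of two is generous, because 7.2 does not name the swallowing instrument.

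**2. What the schedule supports**

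- Appendix A, with its footnotes C and D, schedules XQ, MFI, H&N35 and the mucositis score at Visits 1, 2 and 3 and every three months for a year. That gives a baseline and up to six later visits (Visit 2, Visit 3 and four follow-ups).
- The MD Anderson inventory is named only at Visit 3 in section 6.1. It is absent from the Visit 1 list and from footnote D. It therefore has no scheduled baseline or repeat, and the 7.1 model cannot be fitted to it.
- The Visit 3 text in 6.1 does not name H&N35 or the mucositis score, whereas Appendix A does.
- Toxicity is assessed from Visit 1 through follow-up (Appendix A).

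**3. The plan's own two-group figure (section 7.4)**

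Section 7.2 states no figure. Section 7.4 gives 0.81 SD for exosomes, with 25 per arm, two-sided alpha 0.05 and 80% power. A two-sample t-test calculation gives 0.809 SD, and power at 0.81 SD is 80.1%. The normal approximation gives (1.960 + 0.842) × √(2/25) = 0.792 SD. The figure reproduces.

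**4. Precision of an arm difference in means**

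Half-width of the 95% interval = t(0.975, 2n−2) × √(2/n), in SDs of the quantity compared.

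- n = 25: 2.01 × √(2/25) = 2.01 × 0.283 = 0.57 SD.
- The documents give no dropout rate. Assuming 22, 20, 18 or 15 evaluable per arm gives 0.61, 0.64, 0.68 or 0.75 SD.
- For a change from baseline expressed in single-visit SDs, multiply by √(2(1−ρ)), where ρ is the baseline correlation. Assumed ρ of 0.3, 0.5 and 0.7 gives 0.67, 0.57 and 0.44 SD.
- An analysis that adjusts for baseline as a covariate gives 0.54, 0.49 and 0.41 SD at the same ρ.

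**5. Precision for severe mucositis**

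Section 1.2 cites severe mucositis in 67% and 69% of placebo patients in two trials of radiation plus cisplatin; the midpoint is 68%. With both arms at 68%:

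1.96 × √(2 × 0.68 × 0.32 / 25) = 1.96 × 0.132 = 0.26, or 26 percentage points.

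Against an assumed metformin rate of 50%, 40% or 30%, the half-width is 27, 27 or 26 points, and the power of a test would be 25%, 51% or 78%. This supports reporting estimates with intervals rather than significance claims.

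**6. Safety**

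With no events in 25 patients, the exact two-sided 95% upper limit is 13.7%.

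**The case against.** The strongest defence is that this is a 50-patient pilot feasibility trial, sized for cytokines and exosomes only, which openly declares its secondary analysis descriptive. Section 1.1 speaks only of potential impact. Rewording 2.2 in the same way would remove much of the mismatch without any new analysis. This stands as a reason not to require tests. It does not explain why a descriptive plan names no summary for xerostomia, fatigue or safety.

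Several stronger readings are tempting, and the documents do not support them:

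- A reader might infer that the symptom and safety questions cannot be answered at all. The data are scheduled. For the two named outcomes, arm means and SDs with the numbers analysed would also let a reader derive a crude difference and interval.
- A reader might infer that xerostomia, fatigue and safety are excluded from analysis. The opening sentence of 7.2 nominally covers every secondary outcome, so they are unspecified rather than excluded.
- A reader might object that an ordinal mucositis grade is reduced to means and SDs. Medians and ranges are planned as well.
- A reader might assume that the 7.1 model suits every instrument. It does not suit the dysphagia inventory, which is named at one visit only.

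Two further objections have force. The 67–69% rates are overall incidences under radiation plus cisplatin, whereas this trial takes any radiation candidate and scores mucositis at set visits, so 68% is only illustrative. More estimates also invite over-reading: three instruments at six visits already make 18 intervals before subscales. That is why one key visit should be named in advance.

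**Conclusion.** The point holds as a mismatch between objectives and analysis. Two of five secondary objectives have a named summary and none has a between-arm estimate, so the prespecified analysis does not deliver the effects that 2.2 asks for. The fault is not the lack of hypothesis tests, and the primary analysis is unaffected.

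At full evaluability, the uncertainty left unreported is about ±0.57 SD for a mean difference and, illustratively, ±26 points for severe mucositis. These figures assume 25 evaluable patients per arm and no covariate adjustment; the second also assumes the borrowed 68% rate. They reflect the sample size and would not shrink merely by being reported. The gain is that readers see them. The change should be made, because it mostly uses data already scheduled and a model already in the plan.

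**What to change.** Rewrite 7.2, and the matching text in the Study Summary, as follows. Label everything exploratory, with no significance claims.

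- **XQ, MFI and H&N35:** fit the 7.1 mixed model. Report the arm difference in change from baseline with a 95% interval, with Visit 3 as the key time point and other visits supportive.
- **MD Anderson Dysphagia Inventory:** report the Visit 3 arm difference in means with a 95% interval. State that no baseline is scheduled, and say whether this is the swallowing measure meant in 7.2.
- **WHO mucositis:** report counts by grade and the arm difference in the proportion at grade 3 or higher at scheduled visits, with a 95% interval, beside the planned medians and ranges.
- **Safety and tolerability:** report by arm the number with any CTCAE event of grade 3 or higher and the number permanently stopping study drug, with risk differences and 95% intervals. Describe reaching and holding the target dose in the metformin arm only, because placebo has no escalation (section 5.2).

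Reconcile the Visit 3 instrument list in 6.1 with Appendix A, so that H&N35 and mucositis are clearly collected then. Tie objective response to a stated objective or remove it. Softening 2.2 to descriptive wording would settle part of the mismatch, but xerostomia, fatigue and safety would still need a named summary.

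The cost is plan wording, a few extra tables and several unadjusted exploratory intervals. No new data are needed if the dysphagia inventory stays a Visit 3 comparison and Appendix A is followed.

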## 7.3 Subject Population(s) for Analysis:

All randomized participants with any data will be included in the analysis.

## 7.4 Sample Size Justification

50 subjects will be randomized 1:1 to either metformin or placebo resulting in 25 subjects per group. The standardized difference in means between groups (effect size) that can be detected with 80% power was calculated for various assumptions of the number of cytokines with true differences above the detectable difference using the method of Jung (2005). With at least 5 cytokines out of 40 being different, we have 80% power of detecting a difference for each test if the true difference is at least 1.1 standard deviations.

Detectable difference (D) by number of cytokines with true difference >D assuming 80% power for each test.

| Number of cytokines with true difference >D (K) | Detectable difference in means (D) | Single test alpha | Probability of detecting all K |
|---|------------------------------------|-------------------|--------------------------------|
| 5   | 1.1                                | 0.0060            | 0.33                           |
| 10  | 1.0                                | 0.014             | 0.11                           |
| 15  | 0.9                                | 0.025             | 0.035                          |
| 20  | 0.8                                | 0.042             | 0.012                          |
| 25  | 0.8                                | 0.070             | 0.0038                         |

For the exosome analysis, we have 80% power to detect an effect size of 0.81 (difference in means of 0.81 standard deviations) or greater using a two-sided test with alpha=0.05.

Ref: Jung, S.-H. 2005. Sample size for FDR-control in microarray data analysis. *Bioinformatics*: Vol. 21 no. 14, pp. 3097-3104. Oxford University Press.

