### **2.1 Primary Objective:**

We have chosen a cytokine/chemokine profile analysis as a surrogate marker of trending inflammatory reaction. This response drives the severity of mucositis/xerostomia and acute radiation toxicity. The blood and saliva counts will be compared in the pre-treatment sample, during treatment samples and post treatment samples. Luminex technology with 40 cytokines markers will be used (Luminex technology with the Milliplex MAP Human Cytokine/chemokine Magnetic kit I (41 analytes) (sCD40L, EGF, Eotaxin, FGF-2, Flt-3 ligand, Fractalkine, G-CSF, GM-CSF, GRO, IFN- $\alpha$ 2, IFN- $\gamma$ , IL-1 $\alpha$ , IL-1 $\beta$ , IL-1ra, IL-2, IL-3, IL-4, IL-5, IL-6, IL-7, IL-8, IL-9, IL-10, IL-12 (p40), IL-12 (p70), IL-13, IL-15, IL-17A, IP-10, MCP-1, MCP-3, MDC (CCL22), MIP-1 $\alpha$ , MIP-1 $\beta$ , PDGF-AA, PDGF-AB/BB, RANTES, TGF- $\alpha$ , TNF- $\alpha$ , TNF- $\beta$ , VEGF). Blood and saliva samples will be drawn before, during and immediately after treatment and every three months thereafter for one year. All blood samples will be taken by a phlebotomist who will be blinded as to whether the patient is in the experimental (radiation + metformin) or control (radiation + placebo) groups.

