## **7.0 STATISTICAL PLAN**

### **7.1 Analysis for Primary Outcome**

Mixed effects linear regression will be used to model longitudinal measurements of each cytokine. Measurement time will be treated as a categorical variable and fixed effects in the model will include randomization assignment, time, and randomization by time interaction. A linear contrast will be used to estimate the difference in randomization groups with respect to mean change from baseline to

post-treatment. Significance of this difference will be calculated for each cytokine and p-values will be adjusted using the Benjamini and Hochberg procedure to control the false discovery rate at 5%. Cytokine levels will likely need to be log-transformed prior to analysis to meet model assumptions.

Longitudinal measurements of exosomes will also be modeled using mixed effects linear regression in the same fashion. This analysis is treated as separate from the cytokine questions and the p-value will not be adjusted.

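### Three of the five rows in the 7.4 cytokine power table (K = 15, 20, 25) have about 74%, 63% and 67% power under the Benjamini-Hochberg analysis in 7.1, not the stated 80%.

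*Combined protocol and SAP*

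**What the plan says.** Section 7.1 fits one mixed model per cytokine and tests the difference between arms in mean change from baseline to post-treatment. It then says that "p-values will be adjusted using the Benjamini and Hochberg procedure to control the false discovery rate at 5" per cent. It does not mention estimating the proportion of unaffected cytokines.

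Section 7.4 starts from "50 subjects will be randomized 1:1 to either metformin or placebo resulting in 25 subjects per group". It derives the detectable effect size "for various assumptions of the number of cytokines with true differences above the detectable difference using the method of Jung (2005"). The table has rows for K = 5, 10, 15, 20 and 25 truly different cytokines out of 40, under the caption "Detectable difference (D) by number of cytokines with true difference >D assuming 80% power for each test":

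- Detectable difference D: 1.1, 1.0, 0.9, 0.8, 0.8 SD
- Single-test alpha: 0.0060, 0.014, 0.025, 0.042, 0.070
- "Probability of detecting all K": 0.33, 0.11, 0.035, 0.012, 0.0038

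The only row put into prose is K = 5 at 1.1 SD.

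**The concern.** The alpha column should show the p-value threshold that a cytokine has to pass in the planned analysis. Under BH at 5% that threshold is 0.05 × R/40, where R is the number of cytokines declared different, so it cannot exceed 0.05. The last row prints 0.070. That alone shows that the table was computed for a different rule from the one in 7.1, and a more lenient one.

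This table is the only power justification for the cytokine endpoint. A reader who expects a broad cytokine response (15 or more of 40) would rely on 80% power per cytokine at 0.8 to 0.9 SD.

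**Working it through.** **Inputs.** From 7.4: 25 per arm, 40 tests, 80% power per test, and no allowance for dropout. From 7.1: BH at 5%. Section 7.4 states a two-sided test only for exosomes. I assume it for cytokines, because of the variants tried (two- and one-sided t and z) only the two-sided t-test reproduces all five printed D values.

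**1. Reproducing the table.** At 80% power one expects 0.8K true and (40 − K)α false rejections. Setting the false share to 5% gives

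α = 0.05 × 0.8K / [0.95 × (40 − K)].

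- K = 5: 0.2/33.25 = 0.0060
- K = 25: 1/14.25 = 0.0702
- All five rows: 0.0060, 0.0140, 0.0253, 0.0421, 0.0702, as printed

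The two-sided t-test (48 df, noncentrality D√(25/2)) at 80% power gives D = 1.057, 0.963, 0.894, 0.831 and 0.763, which round to the printed values. The last column is 0.8^K. So all five rows use a rule that takes 40 − K as known.

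**2. The same calculation under BH.** The cutoff is 0.05 × R/40, with expected R = 0.8K + (40 − K)α. Solving for α:

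α = 0.05 × 0.8K / [40 − 0.05 × (40 − K)].

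- K = 15: 0.6/38.75 = 0.0155
- K = 25: 1/39.25 = 0.0255

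**3. A check without simulation.** The R needed for BH to reach a printed alpha is alpha/0.00125.

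- K = 15: 0.025/0.00125 = 20 rejections, when 15 cytokines differ
- K = 20: 0.042/0.00125 = 33.6, so 34 rejections, when 20 differ
- K = 25: 0.070/0.00125 = 56, more than the 40 tests available

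**4. Power under BH.** At a given D, solve α = (0.05/40) × [K × power(D, α) + (40 − K)α].

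| K | Printed alpha | BH cutoff at 80% power | Ratio | Printed D | BH power at printed D | Unrounded D | BH power at unrounded D | D for 80% under BH |
|---|---|---|---|---|---|---|---|---|
| 5 | 0.0060 | 0.0052 | 1.15 | 1.1 | 82.9% | 1.057 | 78% | 1.07 |
| 10 | 0.014 | 0.0104 | 1.35 | 1.0 | 80.3% | 0.963 | 76% | 1.00 |
| 15 | 0.025 | 0.0155 | 1.63 | 0.9 | 73.6% | 0.894 | 73% | 0.95 |
| 20 | 0.042 | 0.0205 | 2.05 | 0.8 | 63.3% | 0.831 | 68% | 0.92 |
| 25 | 0.070 | 0.0255 | 2.75 | 0.8 | 67.4% | 0.763 | 61% | 0.89 |

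(Ratios use the unrounded alphas.) Simulating the BH step-up with 40 independent t-tests agrees with the formula to within half a percentage point in every row. The realised false discovery rate is about 0.05 × (40 − K)/40, that is 3.1%, 2.5% and 1.9% for K = 15, 20 and 25. This is the margin that the table spends and BH does not.

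**5. Method and rounding.** At the unrounded D the loss grows steadily, from 78% at K = 5 to 61% at K = 25. The K = 5 and K = 10 rows reach 80% because D was rounded up. At K = 20, D was rounded down; even the table's own alpha gives only 76.9% at 0.8 SD. Rounding thus explains about 3 to 5 of the 17 missing points there. At K = 25, rounding up hides part of the loss.

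**6. Last column.** In simulation at the printed D, the chance of detecting all K under BH is about 0.02 at K = 15 (0.035 stated). It is below 0.001 at K = 20 and K = 25 (0.012 and 0.0038 stated).

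**7. Correlation.** The documents give none. With an assumed common correlation of 0.3, BH power at the printed D is 82, 79, 71, 61 and 65%; with 0.6 it is 80, 78, 69, 60 and 62%.

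**The case against.** The best defence is that little depends on these rows. This is a pilot feasibility trial with its size fixed at 50. The one power statement in prose (5 of 40, 1.1 SD) has 83% power under BH, and the other rows only illustrate alternative assumptions. That stands, and it keeps the point at the low end of should-fix.

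Second, one-decimal rounding distorts the comparison. This is true row by row, and it is why 74, 63 and 67% do not fall steadily. It does not rescue the three rows, which have 73, 68 and 61% at the unrounded D.

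Third, the table speaks of true differences larger than D, so power at exactly D is a floor. That is correct, but the caption claims 80% as that floor and BH does not supply it.

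Fourth, the analysis is a mixed-model contrast rather than a t-test, so the percentages are approximate. This also stands. Even the more generous normal approximation, which does not reproduce the printed D column, gives 77, 67 and 71%.

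**Conclusion.** The concern holds. All five alphas belong to a rule that knows how many cytokines are unaffected, and 7.1 does not use such a rule. Under the planned BH analysis the K = 15, 20 and 25 rows have about 74, 63 and 67% power against 80% stated. Measured from the printed D, the differences detectable with 80% power are understated by about 0.05, 0.12 and 0.09 SD. The K = 5 and K = 10 rows hold as printed.

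The figures assume 25 analysable patients per arm, all K effects equal to D, 40 independent two-sided t-tests and one BH family of 40. The shortfall in the three rows does not depend on independence. The validity of the 7.1 test is not in question.

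**What to change.** Leave 7.1 as it is and recompute the 7.4 table for BH:

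- D of about 1.07, 1.00, 0.95, 0.92 and 0.89 SD, given to two decimals.
- Expected cutoffs of 0.0052, 0.0104, 0.0155, 0.0205 and 0.0255, labelled as assuming independent cytokines.
- The last column recomputed by simulation. At these D values it is about 0.38, 0.15, 0.06, 0.02 and under 0.01. It is no longer 0.8^K, because the tests share a data-dependent cutoff.

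The K = 5 sentence can stay.

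One added sentence should say which family of tests the table describes. Section 2.1 gives two panel sizes ("Luminex technology with 40 cytokines markers will be used (Luminex technology with the Milliplex MAP Human Cytokine/chemokine Magnetic kit I (41 analytes"), and it also says that "The blood and saliva counts will be compared in the pre-treatment sample, during treatment samples and post treatment samples". Using 41 analytes hardly matters (1.07, 1.00, 0.96, 0.92, 0.90). If blood and saliva are to be pooled in one BH family, the table has to be recomputed for that family.

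If the sponsor would rather keep the present table, 7.1 would have to name a specific procedure that estimates the number of unaffected cytokines, and power would have to be simulated for it. That is a larger change for little gain.

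The cost is a restated table and a clarifying sentence: no extra patients, no change of analysis, and three less favourable detectable differences.

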## 8.0 SAFETY AND ADVERSE EVENTS

### 8.1 Definitions

#### ***Adverse Event***

An ***adverse event*** (AE) is any symptom, sign, illness or experience that develops or worsens in severity during the course of the study. Intercurrent illnesses or injuries should be regarded as adverse events. Abnormal results of diagnostic procedures are considered to be adverse events if the abnormality:

- results in study withdrawal
- is associated with a serious adverse event
- is associated with clinical signs or symptoms
- leads to additional treatment or to further diagnostic tests
- is considered by the investigator to be of clinical significance

